| Month 24, p-value                  |                             |          |        |         | x.xxxx            |                   |

\*Mixed Model: Change from Baseline (BCVA) = Baseline (BCVA) + Treatment + Visit (weeks) + Treatment \* Visit + Subject (random effect)  
CI: Confidence Interval;

**Note to Programmer:** The above table is an example only. Output to be updated to reflect aspects of the final model as appropriate.

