2.1 General considerations

Descriptive statistics will include n (number of observations), mean, standard deviation, median, minimum and maximum for continuous variables, and frequencies and percentages for categorical variables.

The study eye is the eye identified by the investigator according to the protocol inclusion and exclusion criteria and recorded as such at the screening visit in the eCRF.

The efficacy analyses of this study will be based on the study eye data only.

For non-ocular, study eye, and fellow eye summary tables, figures, and listings will be based on all patients included in the analysis/set population under consideration. Unless otherwise specified, all confidence intervals (CIs) and p values will be two-sided and will be based on an alpha significance level of 0.05.

Central Reading Centre data will be used for efficacy summary tables and analyses, whilst all site and Central Reading Centre data will be included in listings.

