2.8.2.3 Handling of missing values/discontinuations in efficacy analyses

For the primary analysis, there will be no imputation for missing data. The mixed model approach where all values recorded for each patient up to the time of withdrawal (or completion) are used is an appropriate model for data missing at random.

Sensitivity analyses will be conducted to explore the robustness of the data to the methods of dealing with missing data. These methods will include LOCF and multiple imputation.

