2.8.2.5 Mixed Modelling

The mixed models to be fitted are detailed in Table 2.8.2.5-1.

Table 2.8.2.5-1 Mixed Models

Model Number	Outcome Variable	Predictor/Covariate		Class Variable		Random Term
		Definite	Optional	Definite	Optional	
MM_1	Change in BCVA from baseline to 2, 12 and 24 months	
 • Treatment • Baseline BCVA • Visit (categorical) • Treatment by Visit Interaction 	
 • Stratification group • Cumulative weeks on treatment 	Treatment Visit Subject		Subject
MM_2	Change in BCVA from baseline to 2, 12 and 24 months	
 • Treatment • Baseline BCVA • Visit (categorical) • Treatment by Visit Interaction 	
 • Injection frequency • Cumulative number of weeks on treatment • Stratification group Baseline: 
 • Age • Lesion size • GA presence • Smoking status • Genotype saliva sample status • Baseline BCVA (<=70/>70) • Baseline IRF • IRF • Baseline SRF • SRF • PED • SRF resolved (y/n) 	Treatment Visit Subject	Stratum Centre	Subject
MM_3	Change in Geographic Atrophy from baseline to 2, 12 and 24 months.	
 • Treatment • Baseline GA area • Visit (categorical) • Treatment by Visit Interaction 	
 • Cumulative number of weeks on treatment Baseline: 
 • Age • BCVA • Injection frequency • Lesion size • GA presence • Smoking status • Genotype saliva sample status • Baseline BCVA (<=70/>70) • Baseline IRF • IRF • Baseline SRF • SRF • PED • SRF resolved (y/n) 	Treatment Visit Subject	Stratum Centre	Subject

Model Number	Outcome Variable	Predictor/Covariate		Class Variable		Random Term
		Definite	Optional	Definite	Optional	
MM_4	Change in CRT from baseline to 2, 12 and 24 months	
 • Treatment • Baseline CRT • Visit (categorical) • Treatment by Visit Interaction 	
 • Injection frequency • Cumulative number of weeks on treatment • Stratification group Baseline: Age 
 • Lesion size • GA presence • Smoking status • Genotype saliva sample status • Baseline BCVA (<=70/>70) • Baseline IRF • IRF • Baseline SRF • SRF • PED • SRF resolved (y/n) 	Treatment Visit Subject	Stratum Centre	Subject

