All results for all patients for will be included for each model, unless otherwise indicated. The repeated nature of the data will be modelled by including subject as random effect. The Kenward-Roger (KR) correction will be used to compute the denominator degrees of freedom to test fixed effects. The least square (LS) mean estimate for intensive retinal fluid treatment group (“intensive”) – relaxed retinal fluid treatment group (“relaxed”) will be obtained for treatment time = 2 months, 12 months and 24 months. These will be obtained with 95% confidence limits.

In regards to primary efficacy, if the upper 2-sided 95% confidence limit for the least square mean for intensive – relaxed mean change in BCVA at 24 months is <5 (the non-inferiority margin) then relaxed will be declared non-inferior to intensive.

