2.12 Sample size and power considerations

This study is designed as a non-inferiority trial. The non-inferiority limit for the difference between groups (change with intensive treatment – change with relaxed treatment) is 5.

Therefore, if the upper 2-sided 95% confidence limit for the difference between treatments (intensive – relaxed) in the change in BCVA (on treatment – baseline) is < 5 the relaxed treatment will be declared non-inferior to the intensive treatment.

Assuming a Standard Deviation (SD) of 15 (as used in the CATT study; Martin et al, 2012) and assuming no true difference between treatments, a sample size of 165 patients per group provides 80% power assuming analysis will be conducted using a t-test. The sample size of 165 per group (total of 330) will be randomised (this allows for 15% drop-out based on the CATT study which observed an 11% dropout in the ranibizumab as needed group and 16% in the bevacizumab as needed group over the two years in the study). Calculations were performed using SAS V9.3.

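### MM_1 adjusts the Month 24 non-inferiority contrast with one baseline-BCVA slope pooled over visits; adding baseline-by-visit is a near-free improvement, not the correction of an error.

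*SAP*

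**What the plan says.** SAP 2.8.2.5 defines MM_1 for change in BCVA at 2, 12 and 24 months. Its definite terms are Treatment and "Baseline BCVA • Visit (categorical) • Treatment by Visit Interaction", with subject as a random effect. The optional terms are stratification group and cumulative weeks on treatment. None of MM_1 to MM_4 has a baseline-by-visit term, definite or optional. The shell for Table 14.2-2 in the Protocol document gives the same single-slope formula, "Change from Baseline (BCVA) = Baseline (BCVA) + Treatment + Visit (weeks) + Treatment" by visit plus a random subject effect, and Table 14.2-3 repeats it for the Per-Protocol Set.

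This model decides the trial. If the upper two-sided 95% limit for intensive minus relaxed at Month 24 "is <5 (the non-inferiority margin) then relaxed will be declared non-inferior to intensive". SAP 2.8.2.3 adds that the mixed model, using every recorded value, "is an appropriate model for data missing at random".

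The documents do not settle which visits are in the model. The MM_1 row names three. SAP 2.8, 2.8.2.3 and 2.8.2.5 speak of all data, values or results, and 2.4.1.3 defines a visit grid that is fortnightly after Week 12.

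**The concern.** The slope of change on baseline at a visit equals (correlation of that visit's BCVA with baseline × SD at the visit ÷ SD at baseline) − 1. It stays constant over two years only if falling correlation is exactly offset by rising spread. With one common slope, the Month 24 contrast is corrected for baseline by an average over earlier visits as well.

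Two things could follow. Part of any chance baseline imbalance between arms stays in the estimate. In addition, the missing-at-random argument needs the mean model to be right at Month 24: if withdrawal depends on baseline vision, and does so differently by arm, a wrong slope can shift the contrast. Both would act on the estimate used for the non-inferiority decision.

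**Working it through.** **The plan's own figure.** SAP 2.12 gives the inputs: "Assuming a Standard Deviation (SD) of 15", "assuming no true difference between treatments", and "a sample size of 165 patients per group provides 80% power assuming analysis will be conducted using a t-test". The margin is 5 letters. All limits are "two-sided and will be based on an alpha significance level of 0.05".
- Evaluable per arm = 2 × (1.960 + 0.842)² × 15² ÷ 5² = 141.3, so 142; the noncentral t version gives 143.
- With 15% dropout, 142 ÷ 0.85 gives 168 and 143 ÷ 0.85 gives 169, while 143 × 1.15 = 164.5 gives exactly 165. The stated figure reproduces within 3%.
- Planning SE with 165 per arm = 15 × √(2/165) = 1.65 letters.

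**Size of the uncorrected imbalance, complete data.** The common-slope and visit-specific estimates differ by (Month 24 slope − pooled slope) × baseline difference between arms. The baseline SD is assumed to be 14 letters, taken from the Total column of the partly filled shell for Table 14.1-10. The chance baseline difference then has SD 14 × √(2/165) = 1.54 letters, and 1.96 SD is 3.02 letters. The correlations and the visit SDs (14/15/16) below are assumptions; the documents give none. The pooled slope is the mean of the three.

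| Correlation with baseline, Months 2/12/24 | Slopes | Pooled | Gap at Month 24 | Shift at 1 SD | Shift at 1.96 SD |
|---|---|---|---|---|---|
| 0.85/0.70/0.60 | −0.15/−0.25/−0.31 | −0.24 | 0.08 | 0.12 | 0.23 |
| 0.90/0.70/0.50 | −0.10/−0.25/−0.43 | −0.26 | 0.17 | 0.26 | 0.51 |

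Variance inflation = (gap × 14)² ÷ (SD₂₄² × (1 − ρ₂₄²)), using unrounded gaps:
- First row: 1.07² ÷ (256 × 0.64) = 0.7%.
- Second row: 2.37² ÷ (256 × 0.75) = 2.9%.
- On the SE these are about 0.3% and 1.4%.

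With correlations 0.85/0.75/0.70 the gap is 0.02 and the shift at 1.96 SD is about 0.05 letter.

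**Simulation.** The set-up was a random-intercept REML fit with and without baseline-by-visit, 1,500 trials per scenario, 165 per arm, about 15% missing at Month 24, SD of change 15 and residual correlation 0.6. Monte Carlo error is about 0.04 letter on bias and 0.4 percentage points on a 2.5% rate.
- Dropout unrelated to baseline: bias is about 0 either way. The SE is 1.67 against 1.66 for slopes −0.2/−0.3/−0.4, and 1.68 against 1.66 for −0.1/−0.3/−0.5.
- Equal slopes of −0.3: SE 1.665 without the term and 1.666 with it, so the term has no visible cost.
- Dropout depending on baseline in opposite directions by arm: the common slope shifts intensive − relaxed by about −0.4 letter (first slope set) and −0.9 letter (second). With a true difference of 5, non-inferiority is declared in 3.4% and 7.1% of trials against a nominal 2.5%. With the term, bias is about 0 and the rates are 1.9% and 1.6%.
- Further runs gave about 0.25 to 0.55 letter when only one arm's dropout depends on baseline and 0.45 to 1.1 letters for opposite directions. They gave essentially no bias when both arms behave alike.

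**Degrees of freedom.** Three visits give 3 − 1 = 2. The derived grid of Weeks 4, 8 and 12, then 14 to 104 by twos, has 3 + 46 = 49 levels, giving 48.

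**The case against.** The case for leaving MM_1 alone is strong. A single baseline covariate with treatment-by-visit is a recognised pre-specified model, and randomisation protects the contrast from average bias when dropout is unrelated to baseline. That stands. The common slope already removes most of an imbalance: 0.24 ÷ 0.31, about three quarters, in the first case and 0.26 ÷ 0.43, about 60%, in the second. The sample size was set for a t-test on change without baseline adjustment, so power is not threatened. Every slope and dropout pattern above is assumed. All of this stands too, and it is why the point is an improvement and not an error.

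It can also be said that the plan covers the matter elsewhere. SAP 2.8.2.2 permits ANCOVAs, which would estimate their own Month 24 slope, and 2.8.2.3 commits to LOCF and multiple imputation. This stands only in part: the ANCOVAs are optional, and neither they nor the sensitivity analyses decide the trial. Refitting the same model to imputed data keeps the common slope.

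A reader might infer more than the documents support:
- That the primary analysis is biased towards non-inferiority. This needs unequal slopes and arm-differential withdrawal by baseline. The documents give only overall dropout rates, and the sign depends on which arm loses which patients.
- That the 63.8 and 61.8 baseline means in the shell for Table 14.1-10 show a real treatment imbalance. Those columns hold 252 and 95 patients, which does not fit 1:1 allocation, and the same figures recur in Table 14.1-11 by genotyping status.
- That the retinal-thickness model MM_4 is affected to a similar degree. It has the same structure, but no effect size for thickness has been worked out.
- That the cost is always 2 degrees of freedom. That holds only for a three-visit model.

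**Conclusion.** The structural observation is certain from the text: one slope for all visits, applied to the contrast that decides non-inferiority. Its consequence in the ordinary case is small: no average bias, about 1% on the SE, and 0.1 to 0.3 letter left uncorrected at a typical imbalance against a 5-letter margin. The bias of roughly 0.25 to 1.1 letters is conditional on assumed visit-specific slopes together with withdrawal that depends on baseline differently by arm. It is a stress case, not a prediction. If the slopes are nearly equal, nothing is gained, but nothing visible is lost either. That balance favours adding the term, and doing so in advance: SAP 2.8.2.2 allows model exploration for fit, so a later addition could look data-driven.

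**What to change.** In SAP Table 2.8.2.5-1, add Baseline BCVA by Visit Interaction to the definite terms of MM_1, and state there which visits enter the model. Update the model footnotes of Tables 14.2-2 and 14.2-3 to match.

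The cost is wording only, with no new data and no change in sample size. The term uses 2 degrees of freedom if Visit means Months 2, 12 and 24, and up to 48 on the full derived grid. Interim visits are sparse there, but a simulation on a 45-visit grid with sparse interim visits also showed no visible loss. The matching term may be added to MM_4, with the Table 14.2-30 footnote, for consistency only.

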**Table 14.2-2 Visual Acuity – Mixed Model Analysis**

Full Analysis Set

|                                    | Random Effects Mixed Model* |          |        |         | Treatment Effects |                   |
|------------------------------------|-----------------------------|----------|--------|---------|-------------------|-------------------|
|                                    | Num d.f.                    | Den d.f. | F-stat | p-value | Intensive (N=X)   | Relaxed (N=X)     |
| Baseline Effect                    | x                           | xx       | x.xx   | x.xxxx  |                   |                   |
| Treatment                          | x                           | xx       | x.xx   | x.xxxx  |                   |                   |
| Visit                              | x                           | xx       | x.xx   | x.xxxx  |                   |                   |
| Treatment*Visit             | x                           | xx       | x.xx   | x.xxxx  |                   |                   |
| Least Squares Means         |                             |          |        |         |                   |                   |
| Month 2 (95% CI)                   |                             |          |        |         | x.xx (x.xx, x.xx) | x.xx (x.xx, x.xx) |
| Month 12 (95% CI)                  |                             |          |        |         | x.xx (x.xx, x.xx) | x.xx (x.xx, x.xx) |
| Month 24 (95% CI)                  |                             |          |        |         | x.xx (x.xx, x.xx) | x.xx (x.xx, x.xx) |
| Treatment Effect            |                             |          |        |         |                   |                   |
| Month 2, Treatment Effect (95%CI)  |                             |          |        |         | x.xx (x.xx,x.xx)  |                   |
| Month 2, p-value                   |                             |          |        |         | x.xxxx            |                   |
| Month 12, Treatment Effect (95%CI) |                             |          |        |         | x.xx (x.xx,x.xx)  |                   |
| Month 12, p-value                  |                             |          |        |         | x.xxxx            |                   |
| Month 24, Treatment Effect (95%CI) |                             |          |        |         | x.xx (x.xx,x.xx)  |                   |

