2.8.2.2 Supportive/Sensitivity Analyses

The primary endpoint will be assessed using a mixed model as described above with no imputation for missing data. Sensitivity analyses may include re-fitting the model with missing data imputed using the LOCF and multiple imputation (as detailed further in Section 2.8.2.3).

In addition, the primary model will be fitted to the Per-Protocol Set as a supporting analysis. Secondary and exploratory models may also be fitted to the Per-Protocol set as supporting or sensitivity analyses.

Secondary endpoints will be assessed with no imputation for missing data. Sensitivity analyses may be conducted; including the re-fitting of models with missing data imputed using the LOCF and multiple imputation, if appropriate. Furthermore, the secondary endpoint models may be fitted to use the Per-Protocol Set as supporting analyses.

Statistical models with optional variables may be explored to identify which model(s) optimally fit the data. In addition, ANCOVAs may be used to confirm cross-sectional analyses, as applicable.

Furthermore, one of the secondary outcomes is to explore the percentage of patients with > 15 letter improvement. This analysis provides a further supporting analysis of the primary endpoint.

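### The primary BCVA model names only a random subject effect, so the Month 24 non-inferiority limit uses a variance pooled over visits; an unstructured covariance would remove that dependence at little cost

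*SAP*

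**What the plan says.** SAP 2.8.2.5 says of the mixed models: "The repeated nature of the data will be modelled by including subject as random effect". In Table 2.8.2.5-1 the outcome of MM_1 is "Change in BCVA from baseline to 2, 12 and 24 months". Its fixed effects are treatment, baseline BCVA, categorical visit and treatment by visit, and Subject is the only entry under Random Term. Degrees of freedom are Kenward-Roger. Non-inferiority is declared if the upper two-sided 95% limit for intensive minus relaxed at Month 24 is below 5 letters.

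The table shells agree. Table 14.2-2 is headed "Random Effects Mixed Model", and the model footnotes of Tables 14.2-2 and 14.2-3 end with "Visit + Subject (random effect". A note to the programmer under each table adds: "The above table is an example only. Output to be updated to reflect aspects of the final model as appropriate".

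Neither document names a residual covariance, visit-specific variances or a robust standard error for MM_1. A robust standard error appears only in SAP 2.8.2.8, for an optional logistic model.

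The supporting analyses in SAP 2.8.2.2 keep the same model: "the primary model will be fitted to the Per-Protocol Set as a supporting analysis", and "Sensitivity analyses may include re-fitting the model with missing data imputed using the LOCF and multiple imputation". A cross-sectional analysis is optional: "ANCOVAs may be used to confirm cross-sectional analyses, as applicable". The sample size in SAP 2.12 assumes a t-test.

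**The concern.** A random intercept with independent residuals implies the same total variance at every visit and the same correlation between any two visits. Because treatment by visit is categorical, the point estimate is specific to Month 24. Its standard error is not: it comes from a variance averaged over the visits in the model.

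If Month 24 spread exceeds that average, the limit is too narrow, and a relaxed regimen that is truly 5 letters worse passes more often than 2.5% of the time. If Month 24 spread is below the average, the limit is too wide and power is lost. Kenward-Roger works inside the assumed covariance and does not correct a wrong one. The t-test behind the sample size uses the spread at the decision visit alone, so the planned analysis and the planned size rest on different variances.

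**Working it through.** **Inputs from the documents.** Margin 5 letters, decided on the upper two-sided 95% limit at Month 24 (SAP 2.8.2.5, 2.12). SD 15, 165 per arm, 15% drop-out, no true difference, t-test, 80% power (SAP 2.12). Subject as the only random term (Table 2.8.2.5-1).

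**Assumed.** All SDs by visit. The documents give none.

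**Step 1: the plan's own figure.** Evaluable patients per arm = 2 × (1.96 + 0.842)² × 15² / 5² = 141.3, so 142. Allowing for 15% drop-out, 142/0.85 = 167.1, so 168, within 3% of the stated 165. Conversely, 165 × 0.85 ≈ 140 per arm gives SE = 15 × √(2/140) = 1.79 and power Φ(5/1.79 − 1.96) = 79.6%. The sample size reproduces and is not affected by this point.

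**Step 2: complete data, three visits.** The compound-symmetry variance is the mean of the three visit variances, so pooled SD = √[(s₂² + s₁₂² + s₂₄²)/3]. The half-width as written is 1.96 × pooled SD × √(2/165); the correct one uses s₂₄. At a true difference of 5, one-sided error = P(Z > 1.96 × pooled SD / s₂₄).

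| Assumed SD, Months 2/12/24 | Pooled SD | Ratio to s₂₄ | Half-width as written | Half-width from s₂₄ | One-sided error |
|---|---|---|---|---|---|
| 15/13/12 | 13.39 | 1.116 | 2.89 | 2.59 | 1.4% |
| 15/15/15 | 15.00 | 1.000 | 3.24 | 3.24 | 2.5% |
| 14/14.5/15 | 14.51 | 0.967 | 3.13 | 3.24 | 2.9% |
| 13/14/15 | 14.02 | 0.935 | 3.03 | 3.24 | 3.3% |
| 8/12/15 | 12.01 | 0.801 | 2.59 | 3.24 | 5.8% |

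For 13/14/15: √[(169 + 196 + 225)/3] = 14.02; 14.02/15 = 0.935; 1.96 × 0.935 = 1.83; P(Z > 1.83) = 3.3%.

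**Step 3: with a baseline covariate and drop-out.** Simulation, 5,000 trials per setting: 165 per arm, 25 per arm missing at random at Month 24, assumed residual correlations 0.6 (Months 2–12), 0.5 (2–24) and 0.75 (12–24), baseline slope −0.4, true difference 5. The SDs here are residual SDs after baseline adjustment. Monte Carlo error is 0.2 to 0.3 points.

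| SDs | Random intercept: mean SE, error | Unstructured: error |
|---|---|---|
| 15/15/15 | 1.73, 2.8% | 2.8% |
| 13/14/15 | 1.61, 3.4% | 2.3% |
| 8/12/15 | 1.37, 6.1% | 2.2% |

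The unstructured SE was about 1.71 to 1.72 in all three settings.

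**Step 4: flat spread with drop-out.** If SD is 15 throughout, correlation decays over time and 15% drop out, equal correlation overstates how much the earlier values of early leavers say about Month 24. With three visits the half-width is at most 1.4% too small (3.41 against 3.46): P(Z > 1.96 × 0.986) = 2.7%. If all visits enter, the largest shortfall is SE 1.728 against 1.785, a ratio of 0.968: P(Z > 1.96 × 0.968) = 2.9%.

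**The case against.** The plan pre-specifies a complete, fittable model with a degrees-of-freedom method and a clear decision rule, and no passage says that BCVA spread changes with time. That stands.

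A reader might infer from the growth rows that the decision rule is anti-conservative. The documents do not support this, because shrinkage is equally compatible with them. Reversing the extreme case to 15/12/8 gives a ratio of 12.01/8 = 1.50 and an error of P(Z > 1.96 × 1.50) ≈ 0.2%. Mild growth moves the error only to about 3%.

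The shells are marked as examples, and the clinical protocol V2 that the SAP cites is not among the documents, so a structure might be named there. This is a fair limit on the finding. However, the sentence in SAP 2.8.2.5 is not marked as an example, and nothing available supplies another structure.

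The tables of mean and SD by visit (shell Tables 11.4-1.1, 11.4-1.2 and 14.2-1) would reveal a changing spread, and an ANCOVA at Month 24 would not pool. But the tables do not enter the decision rule, and the ANCOVA is only optional.

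**Conclusion.** The point holds as a cheap improvement to the primary analysis. The Month 24 limit depends on an average spread over visits that the plan neither justifies nor checks. Under the assumed patterns shown, one-sided error runs from about 1.4% (15/13/12) to 3.3% (13/14/15), with 5.8% only for the extreme 8/12/15. Which pattern applies cannot be known from the documents.

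Two stronger readings should be avoided. One is that the limit can be too narrow only when spread grows: with flat spread, drop-out and decaying correlation a small effect remains, at most about 2.7% with three visits and 2.9% with all visits. The other is that visit-specific variances alone settle the matter: they would leave that effect in place, because it comes from the correlations. Confidence is medium, given the missing SDs by visit and the unavailable clinical protocol.

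**What to change.** For MM_1 with Months 2, 12 and 24, as its outcome row states, replace the random subject term with an unstructured within-subject residual covariance. Do not add it on top of the random term, since the two together are not identifiable. Keep Kenward-Roger. Pre-state a fallback for non-convergence that keeps visit-specific variances without forcing Months 2–12 and 12–24 to share one correlation, for example heterogeneous first-order ante-dependence. Update the Random Term entry for MM_1 in Table 2.8.2.5-1, the sentence in SAP 2.8.2.5, and the footnotes of Tables 14.2-2 and 14.2-3.

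SAP 2.8, 2.8.2.3 and 2.8.2.5 also speak of using all recorded data. If the sponsor means every fortnightly visit to enter, the SAP should say so and name one structure with visit-varying variance and decaying correlation. A random intercept with sandwich standard errors is not a substitute: it repairs the standard error, but under missing-at-random drop-out the Month 24 estimate itself still relies on the covariance being right.

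The cost is SAP text and model code, with 6 covariance parameters (3 variances, 3 correlations) in place of 2. In the simulations above the SE is essentially unchanged if spread is flat (1.73 to 1.72) and rises where Month 24 spread exceeds the average (about 1.61 to 1.71 for 13/14/15), which is where the written limit was too narrow. Restricting the model to three visits does leave out interim values of patients who leave early, which weakens the missing-at-random argument in SAP 2.8.2.3; the sponsor should weigh this when choosing the visits.
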